### 4.2.2 Safety population (apart from thrombotic events)

The population used for safety analyses will be all participants who receive any amount of trial treatment, using data gathered from first administration of trial treatment until up to 120 days after first administration of trial treatment.

### 4.2.3 Thrombotic Event Safety population

## Statistical Analysis Plan

---

The population used for safety analyses of thrombotic events will be all participants who receive any amount of trial treatment, using data gathered from time of consent until 120 days after first administration of trial treatment.

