6.1. Introduction

This trial has an intervention arm and a control arm. These are described in the sections below.

Trial treatment will be started as per randomisation assignment as soon as possible within 24 hours, and no later than 72 hours, of the first recorded platelet count $\leq 30 \times 10^9/L$, or if the participant was admitted with a platelet count already below $30 \times 10^9/L$ as soon as possible within 24 hours, and no later than 72 hours, after the start of chemotherapy or conditioning for a stem cell transplant

The participant's eligibility criteria MUST be rechecked to ensure they are still eligible prior to first administration of the trial treatment.

The period of time between randomisation and initiation of the trial treatment will allow time for pharmacy to prepare and dispense the trial treatment.

During their inpatient stay haematology patients may experience severe nausea and vomiting, diarrhoea, or significant mucositis. This may impair their ability to tolerate or absorb an orally administered medication. Therefore the trial treatment will initially be given by intravenous administration until the participant is well and able to tolerate the oral medication. The treating physician can then switch the medication to its oral formulation. The date on which the participant is switched from IV to oral formulation will be documented. The participant must receive at least one dose of the IV formulation before transferring to oral. Participants can return to IV after commencing oral IMP, this must be documented, but care must be taken to ensure the correct dose is prescribed.

If the participant has not met the stopping criteria when they are ready for discharge oral IMP should be prescribed.

In other patient groups the dose of tranexamic acid is the same whether it is given therapeutically or prophylactically. Due to differences in bioavailability 1g IV is equivalent to 1.5g PO. This dose is similar to the doses given in the three previous RCTs that have been performed (See Investigator Brochure for further information).

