7.2.2. Secondary Safety Outcomes

- Number of thrombotic events from first administration of trial treatment up to and including 120 days after the first dose of trial treatment is administered, per day at risk
- Number of participants developing Venous Occlusive Disease (VOD; Sinusoidal obstructive syndrome, SOS) within 60 days of first administration of trial treatment
- All-cause mortality during the first 30 days and the first 120 days after the first dose of trial treatment is administered
- Death due to thrombosis during the first 120 days after the first dose of trial treatment is administered
- Death due to bleeding during the first 30 days after the first dose of trial treatment is administered
- Number of serious adverse events from first administration of trial treatment until 60 days after the first dose of trial treatment is administered

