The main primary outcome analysis will be based on the mITT population. However, a per-protocol analysis of the primary outcome will also be performed. This per-protocol analysis will exclude all participants who were randomised in error and all participants who did not adhere to a set of minimum compliance criteria during the first 30 days of the trial. The criteria are:

- The participant commenced trial treatment within 72 hours of the first recorded platelet count $\leq 30 \times 10^9/L$, OR if the participant was admitted with a platelet count already below $30 \times 10^9/L$ within 72 hours after the start of chemotherapy or conditioning for a stem cell transplant.
- The participant received trial treatment and only received the trial treatment prescribed to them and did not receive open label tranexamic acid, other antifibrinolytic agent or procoagulant drug
- The participant only received the correct dose of the trial treatment prescribed to them
- The participant did not receive trial treatment after the point at which discontinuation of trial treatment should have occurred

Participants who did not meet all the eligibility criteria and/or met at least one of the exclusion criteria will be considered as randomised in error.

- **Safety population (apart from thrombotic events)**

The population used for safety analyses will be all participants who receive any amount of trial treatment, using data gathered from first administration of trial treatment until up to 120 days after first administration of trial treatment.

- **Thrombotic Event Safety population**

The population used for safety analyses of thrombotic events will be all participants who receive any amount of trial treatment, using data gathered from time of randomisation until 120 days after first administration of trial treatment.

- **Stopping rules**

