### Safety outcomes

- Number of thrombotic events from first administration of trial treatment up to and including 120 days after the first dose of trial treatment is received, per day at risk, will be described by arm.
- Number of participants developing Veno-occlusive Disease (VOD; Sinusoidal obstructive syndrome, SOS) within 60 days of first administration of trial treatment, will be described by arm.
- All-cause mortality during the first 30 days and 120 days after the first dose of trial treatment is administered will be estimated by the Kaplan-Meier method and compared using Cox regression analysis. Participants withdrawn or lost to follow up before day 30/day 120 will be censored at the time that they withdrew/were lost to follow up.
- Death due to thrombosis during the first 120 days after the first dose of trial treatment is administered will be estimated using the cumulative incidence function, with the competing risk of death due to other causes. To accommodate a random centre effect, Cox regression analysis will be used to compare death due to thrombosis between treatment arms. Participants who have not died will be censored at day 120 or at the point of last contact, whichever is first. Participants who died prior to day 120 from other causes will be censored at the time of death. If numbers of deaths due to thrombosis are very small, the number of deaths will simply be described by arm.
- Death due to bleeding during the first 30 days after the first administration of trial treatment is received will be estimated using the cumulative incidence function, with the competing risk of death due to other causes. To accommodate a random centre effect, Cox regression analysis will be used to compare death due to bleeding between treatment arms. Participants who have not died will be censored at day 120 or at the point of last contact, whichever is first. Participants who died prior to day 120 from other causes will be censored at the time of death. If numbers of deaths due to bleeding are very small, the number of deaths will simply be described by arm.
- Number of serious adverse events from first administration of trial treatment until 60 days after the first dose of trial treatment is administered, per day at risk, will be summarised by arm, including number of symptomatic thrombotic events (venous thromboembolisms and arterial ischaemic events), veno-occlusive disease, sepsis, organ failure and deaths.

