**Table xx      Safety data summary - data are numbers**

## Statistical Analysis Plan

Outcome	Active arm (n=)	Placebo arm (n=)	Overall (n=)
Total number of serious adverse events (SAE) up to day 60			
Sepsis			
Organ failure			
GvHD			
Transfusion reaction			
Fever			
Other SAEs			
Number of participants experiencing at least one SAE			
Symptomatic thrombotic events up to day 120			
Venous thromboembolisms			
Arterial ischaemic events			
Veno-occlusive disease up to day 120			
Unexpected adverse reactions up to day 60			
Deaths up to day 120			

All SAEs, unexpected adverse reactions, thrombotic events and veno-occlusive disease are reported in full in Appendix 1.

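### Thrombotic safety analysis has three conflicting start points: consent (SAP populations), randomisation (protocol population) and first dose (the outcome itself)

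*SAP*

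**What the plan says.** The outcome is the same in both documents. Protocol 7.2.2 gives "Number of thrombotic events from first administration of trial treatment up to and including 120 days after the first dose", and SAP 4.4 opens with the same start, "Number of thrombotic events from first administration of trial treatment up to and including 120 days", adding that the number, "per day at risk, will be described by arm". The protocol synopsis, Protocol 11.5.1, SAP 2.2.2 and the safety outcomes table in SAP 5.5 agree.

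The analysis populations do not. SAP 4.2.3 takes "all participants who receive any amount of trial treatment", "using data gathered from time of consent until 120 days after first administration of trial treatment", and SAP 4.1 repeats this for the interim report to the Data Monitoring Committee (DMC). Protocol 11.4 has the same population, but "using data gathered from time of randomisation until 120 days after first administration of trial treatment".

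The safety summary tables in SAP 5.1 (interim) and SAP 5.5 (final) have a row reading "Symptomatic thrombotic events up to day 120", with no start.

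Past or current thromboembolic disease is the first exclusion criterion in Protocol 4.2. Protocol 6.1 says the participant's "eligibility criteria MUST be rechecked to ensure they are still eligible prior to first administration of the trial treatment", and SAP 3.1 makes the recheck form mandatory on day 1.

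**The concern.** Three starts for one outcome leave the analyst to choose. Thromboembolism is one of two outcomes that Protocol 9.4 calls the main safety outcomes of interest. Both documents justify continuing past an efficacy signal partly by the low power for thromboembolic events. With so few events expected, the window should not be open to interpretation.

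The two earlier starts also do not suit a treated-only population. Anyone whose thrombosis is diagnosed before dosing should fail the recheck, stay untreated and never enter. The added days are therefore event-free by selection (immortal time). They cannot supply a background rate, and counting them as time at risk lowers the reported rate. An event that enters despite the recheck precedes the drug under study.

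**Working it through.** **The texts side by side**

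| Start of window | Where |
|---|---|
| Consent | SAP 4.1 (interim); SAP 4.2.3; also the Form 19 completion window in SAP 3.1 |
| Randomisation | Protocol 11.4 |
| First administration | Protocol synopsis, 7.2.2, 11.5.1; SAP 2.2.2, 4.4, safety outcomes table in 5.5 |
| Not stated | Safety summary tables, SAP 5.1 and 5.5 |

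All of this is current text. The SAP contradicts both the protocol and itself.

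**Is the population text an analysis rule?** SAP 4.2.2 uses the same sentence form to set the window for all other safety outcomes, from first administration. The separate thrombotic population has the same participants and differs only in its earlier start. It therefore reads as an analysis window, not just a note on data collection.

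**The plan's own figure.** Protocol 11.3.3 and SAP 1.5.3 state that observed venous thromboembolism of 3.6% on placebo and 5% on tranexamic acid (TXA), with 616 participants, gives a 95% confidence interval that excludes a relative risk of 3.5. With 308 per arm:
- Expected events: 308 × 0.036 = 11.1 and 308 × 0.05 = 15.4.
- Relative risk = 0.05/0.036 = 1.39.
- SE(log RR) = √(0.95/15.4 + 0.964/11.1) ≈ 0.386.
- 95% CI = exp(ln 1.39 ± 1.96 × 0.386) = 0.65 to 2.96.

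The statement reproduces and does not depend on the start date.

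**Dilution if pre-dose days enter the denominator.** Assume one event per participant at these frequencies, full 120-day follow-up, no pre-dose events, and d pre-dose days for everyone. The rate is multiplied by 120/(120+d).
- d = 0: 0.036/120 and 0.05/120, i.e. 0.300 and 0.417 per 1,000 days.
- d = 7: 120/127 = 0.945, 5.5% lower.
- d = 14: 120/134 = 0.896, 10.4% lower.
- d = 28: 120/148 = 0.811, 18.9% lower.

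The range of d is assumed. The 72-hour limit in Protocol 6.2.4 runs from the qualifying platelet count, or from the start of chemotherapy or conditioning, and not from consent. Protocol 4.1 admits patients whose chemotherapy is only planned. The factor cancels in the rate ratio, which stays at 1.39 when d is equal in both arms.

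**A pre-dose event that enters by deviation.** SAP 4.2.1 foresees participants randomised in error who are still treated. From 15.4/11.1 = 1.39:
- One extra event in each arm: 16.4/12.1 = 1.36.
- One in the TXA arm only: 16.4/11.1 = 1.48.
- One in the placebo arm only: 15.4/12.1 = 1.27.

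The direction depends on the arm in which the event falls. All three values lie well inside 0.65 to 2.96.

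**The case against.** The best defence is that the only rate the plan specifies already runs from first dose, wherever the outcome is defined or analysed. On that reading the population text says which data are gathered, and nowhere says that consent-to-dose days count as days at risk. Collecting from consent is sensible in itself. This largely stands: dilution is conditional on the population text governing the denominator. The conflict remains, because the parallel sentence in SAP 4.2.2 does set an analysis window, and at the interim SAP 4.1 is the text that sets one.

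The summary tables report numbers, not rates. If pre-dose time is event-free, their counts are the same under all three starts. The SAP schedules also define Day 1 as the first day of treatment, so the unlabelled rows can be read as study days 1 to 120. This stands too: the counts can differ only if someone is dosed despite a pre-dose thrombosis.

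A reader might go further and infer that both rates are too low as written, or that any pre-dose event pulls the comparison towards no difference. The documents support neither. The first requires the population text to override the outcome definition. The second is true only of additions balanced across arms, as 1.48 against 1.39 shows.

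**Conclusion.** The inconsistency is real and concerns a main safety outcome, but its demonstrated effect is limited. If pre-dose days are counted, both arms' rates fall by 120/(120+d), for example 5.5% at an assumed 7 days and 10.4% at 14. If a pre-dose event enters by deviation, it is counted against a drug not yet given, and the interim or final summary count could differ from the final outcome row.

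The finding should not be read as bias between arms. The extra time precedes blinded treatment, so no systematic difference is expected. The outcome is only described by arm, so no test or power figure changes, and the relative-risk statement of 3.5 is unaffected.

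That pre-dose time is event-free rests on the recheck being applied and on events diagnosed before dosing.

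The same summary tables count veno-occlusive disease to day 120, while the outcome is 60 days. That is a labelling mismatch and no reason to discard safety counts.

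**What to change.** - In SAP 4.1, SAP 4.2.3 and Protocol 11.4, set the thrombotic analysis window to run from first administration up to and including 120 days after it, for both events and days at risk.
- Keep collecting from consent on Form 19, and list any events between consent and first dose separately. The thrombotic listing in SAP Appendix 1 shows no date column; add one, or confirm that event dates are held, so that the split can be made.
- Label the thrombotic rows of the interim and final summary tables as running from first dose to day 120.
- In the same tables, show veno-occlusive disease to day 60 to match the outcome. A day-120 count can stay as a clearly labelled additional row.
- If the interim analysis has already been reported, state which window it used.

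The cost is a minor wording amendment to both documents, through the route in Protocol section 18. No new data collection is proposed, provided event dates are already recorded.

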### 4.3 Analysis of primary outcome measures

#### **Primary efficacy analysis**

The proportion of participants who die or have bleeding of grade 2 or above by WHO criteria during the first 30 days from the day the first dose of trial treatment is administered, will be estimated by the Kaplan-Meier method and compared by treatment arm using Cox regression analysis. All participants whose platelet count dropped to  $30 \times 10^9/L$  or below, regardless of length of follow-up will be included. Participants withdrawn or lost to follow up before day 30 will be censored at the time that they withdrew/were lost to follow up. Any missing bleeding assessments during the 30-day follow up period or to the last point of contact, whichever is first, will be assumed to be grade 1 or below.

If there is evidence of a difference in the primary outcome between treatment arms, the number needed to treat (NNT) (for benefit) will be presented. NNT is the number of participants who need to be treated with tranexamic acid in addition to standard care in order for one additional participant to benefit. It is calculated as  $1 / (\text{difference in proportion experiencing the primary outcome in each treatment arm as a decimal})$ .

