	
Trial treatment will be started as per randomisation assignment. Either as soon as possible within 24 hours, and no later than 72 hours, of the first recorded platelet count $\leq 30 \times 10^9/L$, OR if the participant was admitted with a platelet count already below $30 \times 10^9/L$ as soon as possible within 24 hours, and no later than 72 hours after the start of chemotherapy or conditioning for a stem cell transplant.
 
All participants will start with Intravenous administration
 
The trial treatment (Tranexamic acid 1g/placebo) will be administered intravenously as a slow IV bolus over 10 minutes every 8 hours.
 
If the participant is well enough they can switch to:
 
Oral administration
 
The trial treatment (Tranexamic acid 1.5g/placebo) will be administered orally as 3 X 500mg tablets every 8 hours.

Trial hypothesis	
The hypothesis is that in patients with haematological malignancies, during a period of severe thrombocytopenia, prophylactic use of antifibrinolytics will decrease bleeding or death and the demand for platelet transfusions.

Primary outcome measure(s)	
Primary Outcome
 
Estimated proportion of participants who died or had bleeding of WHO grade 2 or above during the first 30 days of the trial. Starting from the first administration of trial treatment

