8.2. Procedures for Assessing Efficacy

8.2.1. Bleeding Assessment

Bleeding assessment will commence when the participant is randomised and stopped when one of the following occurs:

- It has been 30 days since the trial treatment was commenced
- Or in those cases where trial treatment was *not* started, 30 days from platelet count $\leq 30 \times 10^9/L$ or the commencement of chemotherapy/stem cell conditioning therapy
- The participant dies.
- Participant withdraws his/her consent to having bleeding assessments performed.
- Site investigator withdraws the participant from all further study assessments.

Bleeding assessments will be conducted using a tool based upon that used in the recent TOPPS trial ([20](#)) and further developed by an international working group – the BEST collaborative ([46](#)). If a participant is an out-patient between day of randomisation and trial treatment starting they will be asked to inform the research team if they have had any bleeding at home. Simple guidance notes will be provided to assist with this.

Rates of recorded bleeding are known to vary considerably between trials. Reasons for this variability have been explored and published through a review organised by the BEST collaboration, and include different patient groups and bleeding definitions, and variable follow up periods ([39](#)).

In the TREATT trial, a number of measures will be taken to standardise documentation and recording of bleeding, including trained assessors, monitoring and education. In the recent TOPPS ([20](#)) trial, where completeness of bleeding outcome documentation was excellent, a bleeding assessment was completed on 93% (8405/9030) of days for patients in the no-prophylaxis group, and 97% (8733/8970) of days in the prophylaxis group. The majority of patients in both arms had bleeding information collected on each trial day (median no-prophylaxis 30 days (IQR 29 to 30); median prophylaxis 30 days (IQR 30 to 30)).

For inpatients, bleeding assessments will be performed using the bleeding assessment tool which includes a physical assessment of the participant, patient interview (if possible) and review of patient chart and laboratory data. Research staff will perform the physical assessment and interview before reviewing the participant's charts, medical notes and

laboratory data to allow an objective assessment. Research staff will perform the bleeding assessment at approximately the same time each day.

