11.4. Interim Monitoring and Analyses

TREATT proposes to investigate the efficacy and safety of anti-fibrinolytic therapy in thrombocytopenic patients. In order to better address the often urgent nature of treatment administration, patients will be randomised earlier (when the platelet count is less than $50 \times 10^9/L$) than when the trial treatment is administered (when the platelet count is less than $30 \times 10^9/L$). The TREATT investigators have thus identified separate analysis populations to test the trial hypotheses.

Analysis Populations

- **Efficacy population**

The population used for efficacy analyses will be a modified intent to treat population (mITT) including all eligible randomised patients whose platelet count falls to $30 \times 10^9/L$ or below. Data gathered for 30 days from the time the first dose of trial treatment is administered, or is planned to be administered for those participants who did not receive treatment. Randomised participants whose platelet counts do not fall to $30 \times 10^9/L$ or below will be excluded from the analysis, as will participants who develop exclusion criteria prior to their count falling to $30 \times 10^9/L$ or below. These exclusions are deemed appropriate as the early randomisation is for pragmatic reasons only. Characteristics of all randomised patients will be compared to the mITT population to ensure that excluded participants are similar across the arms.

Unless otherwise specified, all analyses will be by this mITT. All subjects who fulfil the mITT requirements will be included in the analyses, in the treatment group to which they were randomly assigned. Subjects who were prescribed trial treatment will be included in the analyses, even if they stop trial treatment “early”, or receive prophylactic transfusions not in accordance with the protocol.

Rationale: Owing to the emergent nature of treatment of thrombocytopenic patients, participants are randomised in a double blind fashion to the treatment arms when platelet levels drop below $50 \times 10^9/L$. This will allow time for the pharmacy to prepare the trial treatment, and for the trial treatment to be available when the platelet count falls to $30 \times 10^9/L$ or below. This has been instituted for pragmatic reasons and will guard against delays in the availability of the trial treatment.

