General	Bleeding that does not fulfil the requirements for grade 2 bleeding. Please see examples in organ-specific categories below.	Any bleeding that does not fulfil the requirements for grade 3 bleeding BUT requires an intervention or treatment: Examples of Interventions - Nasal Packing - Bladder irrigation Examples of treatments - Platelet transfusion given to treat active bleeding and NOT given only because the platelet count is below the prophylactic platelet transfusion trigger - Medications prescribed to treat bleeding	Any bleeding that does not fulfil the criteria for grade 4 bleeding BUT requires: Red cell transfusion specifically related to treatment of bleeding within 24 hours of onset of bleeding. OR A significant intervention, for example: - Endoscopy to treat the bleeding - Interventional radiography to treat the bleeding - Transfer to the operating theatre/ room for treatment of bleeding	Any bleeding that is fatal or life threatening. For example: - Bleeding that requires transfer to intensive care/treatment unit - Bleeding that is associated with haemodynamic instability and causes inadequate tissue perfusion (for further clarification see general guideline above).
Oral and nasal†	Spontaneous oropharyngeal bleeding - total duration of all episodes in previous 24 hours < 30 minutes* Traumatic oropharyngeal bleeding e.g. after bites to lips and tongue lasting > 10 minutes or interfering with daily activities Epistaxis - total duration of all episodes in previous 24 hours < 30 minutes*	Oropharyngeal bleeding – total duration of all episodes in previous 24 hours > 30 minutes* Epistaxis – total duration of all episodes in previous 24 hours > 30 minutes*		Any bleeding that requires intubation to protect the airway

	Petechiae of oral mucosa ≤ 25%	Petechiae of oral mucosa > 25%		
Skin†	Petechiae (< 3mm diameter), purpura (3mm to 10mm diameter) or bruising covering ≤ 25% of skin (1 arm = 9%; 1 leg = 18%; trunk = 36%; head = 9%; genitalia 1%)	Petechiae, purpura (3mm to 10mm diameter) or bruising covering > 25% of skin ((1 arm = 9%; 1 leg = 18%; trunk = 36%; head = 9%; genitalia 1%)		

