## 2. Outcome Measures

### 2.1 Primary outcome measures

Estimated proportion of participants who died or had bleeding of WHO grade 2 or above during the first 30 days of the trial **from the first day of administration of the study intervention.**

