## Statistical Analysis Plan

Imputation will be performed using multiple imputation by fully conditional specification (Van Buuren, 2007), with the number of imputations equal to the percentage of missing data.

- Number of days between platelet count first  $30 \times 10^9/L$  or below OR if the participant was admitted with a platelet count already below  $30 \times 10^9/L$ , number of days between the start of chemotherapy or conditioning for a stem cell transplant, and start of trial treatment, or planned start for those participants who did not receive treatment, will be summarised by treatment arm, for all participants included in the mITT analysis. It is important to monitor this since the 30-day analysis period only begins at the start of study treatment.
- Number of bleeds between platelet count first  $30 \times 10^9/L$  or below and start of trial treatment or planned start for those participants who did not receive treatment will be summarised by treatment arm, for all participants included in the mITT analysis. It is important to monitor whether any bleeds occurred prior to the start of the 30-day analysis period.

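### The primary analysis does not separate grade 2+ bleeding already present before the first dose from new bleeding, which dilutes the estimated prophylactic effect in both arms alike

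*SAP*

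**What the plan says.** **Time origin.** SAP 2.1 defines the outcome as "Estimated proportion of participants who died or had bleeding of WHO grade 2 or above during the first 30 days of the trial", counted from the first day of administration. SAP 4.3 repeats the day-based origin: "during the first 30 days from the day the first dose of trial treatment is administered". Protocol 7.1 also uses the first day of treatment. The Protocol synopsis says "Starting from the first administration of trial treatment", and Protocol 11.4 says "Data gathered for 30 days from the time the first dose of trial treatment is administered".

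**Delay to dosing.** Participants are randomised at a platelet count of 50 x 10^9/L or below. The first dose may follow the first count of 30 or below by up to 72 hours. For those admitted already low, it may follow the start of chemotherapy or conditioning by up to 72 hours (Protocol 6.1, SAP 1.3).

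**Bleeding data.** Protocol 8.2.1: "Bleeding assessment will commence when the participant is randomised". Inpatients are assessed once a day at about the same time. SAP Table 1 has Form 7 completed from the day of randomisation.

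**Grading.** In Protocol 20.2 the grade 2 criterion for oropharyngeal bleeding and for epistaxis is "total duration of all episodes in previous 24 hours > 30 minutes". Invasive-site oozing has a similar 24-hour look-back. A footnote says that skin and oral petechiae, purpura, ecchymoses, oral blood blisters and subconjunctival haemorrhage do not count on a day when they are no worse than the day before. The footnote is still marked as for discussion. Grades are assigned centrally by a computer algorithm (Protocol 8.2.2), which is listed in the SAP references but not supplied.

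**Pre-dose bleeds.** SAP 4.7 summarises bleeds between the first count of 30 or below and the start of treatment, by arm, and gives the reason: "It is important to monitor whether any bleeds occurred prior to the start of the 30-day analysis period". The table shell in SAP 5.9 reports these as mean (SD), with a separate row for grade 2 or above.

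**The concern.** The trial asks whether tranexamic acid prevents bleeding. A bleed that began before the first dose cannot be prevented by it. Such a bleed can enter the primary outcome in two ways. A grade 2 bleed outside the footnote's list may continue into Day 1 and be scored there. Or a bleed in the hours before the dose may be captured by a Day 1 assessment that looks back 24 hours or takes place before the dose.

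Nothing in SAP 4.3 or 4.7 removes, adjusts for or tests the effect of these events. The tabulation is descriptive. It counts bleeds per arm, not participants bleeding at first dose, and does not say where a Day 1 pre-dose bleed is placed.

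Randomisation is blinded, so these events should fall equally in the two arms. At stake are the size of the risk difference, the number needed to treat derived from it, and power.

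**Working it through.** **Inputs.** 43% against 32%, two-sided 0.05, 80% power, log-rank test, 586 required before the 5% addition (Protocol 11.3.2, SAP 1.5.2). The prevalence q of grade 2+ bleeding already present at first dose is not in the documents; 2%, 5% and 10% are assumptions.

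**Step 1: reproduce the plan's figure.**
- HR = ln(0.68)/ln(0.57) = 0.686, and ln HR = -0.377.
- Events = 4 x (1.96 + 0.842)^2 / 0.377^2 = about 221.
- Mean event probability = (0.43 + 0.32)/2 = 0.375, so N = 221.2/0.375 = 590, against the stated 586.
- Power with 586: 586 x 0.375 = 219.75 events, which gives 79.7%.

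The sample size is therefore not in error for the effect it assumes.

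**Step 2: dilute the effect.** Prevalent bleeds have hazard ratio 1 and new bleeds 0.686. Let m be the probability, averaged over arms, of an event that is not a prevalent bleed. The average log hazard ratio is ln(0.686) x w, with w = m/(q + m). Events d = 586 x (q + m). Power = Φ(√d x |average log HR|/2 - 1.96).

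Two readings are possible.
- *Included:* the 43% already contains q. The remaining placebo risk is r0 = (0.43 - q)/(1 - q), and the treated risk is r1 = 1 - (1 - r0)^0.686.
- *On top:* q is added to 43% and 32% among the rest, so the difference is (1 - q) x 11 points.

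Worked case, included, q = 5%:
- r0 = 0.38/0.95 = 0.400 and r1 = 1 - 0.600^0.686 = 0.296.
- Treated total = 0.05 + 0.95 x 0.296 = 0.331, so the difference is 9.9 points.
- m = 0.95 x (0.400 + 0.296)/2 = 0.330 and w = 0.330/0.380 = 0.869.
- d = 586 x 0.380 = 223 and the average log HR is -0.327.
- Power = 68.5%.

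| q (assumed) | Included: difference | Included: power | N for 80% | On top: difference | On top: power |
|---|---|---|---|---|---|
| 0% | 11.0 | 79.7% | 590 | 11.0 | 79.7% |
| 2% | 10.6 | 75.6% | 654 | 10.8 | 76.8% |
| 5% | 9.9 | 68.5% | 771 | 10.4 | 72.2% |
| 10% | 8.8 | 55.5% | 1044 | 9.9 | 64.3% |

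**Step 3: what the remedies recover.** Excluding participants with a prevalent bleed gives power of 77.8%, 74.6% and 68.4% (included) or 78.9%, 77.7% and 75.5% (on top) at 2%, 5% and 10%.

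Keeping everyone and stratifying the log-rank test on a pre-dose bleeding flag was simulated under the included reading. With a perfect flag the gain is about 2, 6 and 13 points of power. With an assumed flag of 60% sensitivity and 3% false positives it is about 1, 2 and 5 points. A realistic flag misses bleeds that start between the last assessment and the dose, and it marks some that have stopped.

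**The case against.** **Relief exists.** A reader might infer that the plan makes no allowance for pre-dose bleeding. The documents do not support that. The footnote removes unchanged skin, oral and subconjunctival signs. Visible haematuria is an exclusion, and Protocol 6.1 requires eligibility to be rechecked before the first dose. Pre-dose bleeds are reported by arm. This stands, but the footnote is unsettled and none of it covers continuing melaena, epistaxis or haemoptysis.

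**The origin is not a simple SAP departure.** A reader might infer that the SAP contradicts the Protocol. Protocol 7.1 uses the day, as the SAP does; the synopsis and 11.4 use the dose. The wording is mixed within the Protocol itself. With one assessment a day, a day-based clock is also close to the resolution of the data.

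**The algorithm may already handle it.** That cannot be checked, so it cannot be said flatly that every continuing bleed is scored again on Day 1. If a rule exists, the SAP should state it.

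**The prevalence is unknown.** It is tempting to scale the 17% bleeding rate that Protocol 1.2 quotes from another trial (17% x 43/70, about 10%). That figure covers morning counts of 6 to 80 x 10^9/L and does not describe status before a first dose, so it cannot anchor the range.

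**Counting all bleeding from Day 1 is defensible.** The SAP's stated aim is that tranexamic acid reduces bleeding, and the dilution cannot create a false positive. This argues for leaving the primary outcome definition alone. It does not argue against a sensitivity analysis.

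**Conclusion.** The concern holds in limited form. The primary analysis can count grade 2+ bleeds that predate treatment, and no planned analysis shows how much they matter. The consequence is dilution and lost power in both arms alike; the documents give no ground for inferring bias towards either arm or an error in the sample size.

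The size rests on assumed prevalence. Over 2-10%, the difference falls from 11.0 points to between 10.6 and 8.8 (included) or between 10.8 and 9.9 (on top). Power falls from about 80% to between 76% and 56%, or between 77% and 64%. At the low end the loss is about 3 to 4 points. The calculation also assumes that the drug has no effect on bleeds already present and its planned effect on all others.

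A reader might infer that adjusting the Cox model would repair the primary result. It would not: the Kaplan-Meier risk difference and the number needed to treat stay diluted. Only the new-bleeding analysis addresses those. This is a cheap improvement, not a flaw that invalidates the primary analysis.

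**What to change.** 1. **SAP 4.7.** Keep the tabulation and add a prespecified sensitivity analysis of the primary outcome, with risk difference and number needed to treat. Count death, or grade 2+ bleeding that is new or worsened after the first dose. Exclude participants with a grade 2+ bleed at the last pre-dose assessment. If clock times for dose and assessment are unavailable, start counting bleeds at the Day 2 assessment. For untreated mITT participants, use the planned first-dose day, as SAP 4.2.1 already does for the data window.
2. **SAP 4.3.** Adjust the Cox model for grade 2+ bleeding at the last Form 7 assessment before the first dose (yes/no, with no earlier assessment coded as no). Everyone stays in the mITT. Expect to recover about 1 to 13 points of power, depending on prevalence and flag accuracy.
3. **Definitions.** Settle the footnote in Protocol 20.2 that is marked for discussion. State one time origin across the Protocol synopsis, 7.1 and 11.4 and SAP 4.3. If the grading algorithm has a carry-over rule, write it into the SAP.

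**Cost.** One derived variable from data already collected, some SAP wording, and a hazard ratio that becomes conditional on pre-dose bleeding. The sensitivity analysis has slightly fewer participants and may drop some true bleeds soon after the first dose. The flag will be weaker for outpatients, who before treatment starts are only asked to report bleeding at home, and for those randomised and dosed on the same day.
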